#### 8.2 Investigational device and comparators

#### 8.2.1 EDDI

EDDI is used to measure sEMG, and detect GTC seizures based on this signal. For this purpose an EDDI is used on biceps of one of the upper arms. The electrode is placed on the outer side of the biceps as shown in the IFU.

#### **8.2.2 Comparators**

The alarms of the EDDI are compared to the physician's interpretation of when GTC seizures have occurred. This interpretation is based on both EEG measurements and video surveillance.

#### 8.3 Subjects

Subjects will be selected among patients who are signed up for hospitalized at specialized epilepsy centers for another reason than participation in this study (e.g. to investigate suspected epilepsy or to improve

their epilepsy diagnosis and treatment). Subjects are to fulfill the in- and not the exclusion criteria listed in section 3.5.3.1 and 3.5.3.2 respectively.

Subjects will be asked whether they would be interested in participating in the study at the preliminary consultation before the video-EEG monitoring. Patients will receive written information about the project. Those patients who will be interested in participating in the study will be called to an information meeting, where they can also take an accompanying person with them.

Subjects will participate in the investigation for the duration of their hospitalization (maximum 4 days). Prior to the hospitalization and enrollment into the investigation, subjects are to give their consent to participate as described in section 15.

Total number of subjects to be included is expected to be approximately 80. From these included patients only those with either epileptic GTC seizures or non-epileptic convulsive seizures (PNES) are included in the final evaluation of the EDDI.

The first patient is expected to be included in February 2014 and the last patient is expected to end participation in October 2014 or when the planned number of patients has been included.

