#### 3.3 Test design

The current clinical investigation will use the algorithm developed in the DK007-ME investigation. It will be conducted as a double-blinded clinical investigation assessing the sensitivity and specificity of EDDI, an epilepsy alarm, for detection of GTC seizures in patients with epilepsy. The double-blinded part will be between the physicians annotating when GTC seizures exists based on EEG and video, the gold standard, and the epilepsy alarm, which annotates when GTC seizures exist based on the EMG signal.

Patients will be hospitalized at a specialized epilepsy center either to investigate suspected epilepsy or to improve their epilepsy diagnosis and treatment. During their hospitalization patients will at least be monitored by the gold standard: video monitoring and EEG.

In this investigation, approximately 20 patients with GTC seizures will be needed, along with approximately 10 patients with PNES. This means that probably 70-80 patients in total will be included and equipped with an EDDI, after providing their informed consent. The Epilepsy Alarm should be placed on one of the upper arms (the outer side of biceps) as shown in the IFU for the device. It will need to be replaced with a new electrode every 24 hours. After a maximum of 4 days, the patient will be discharged from the hospital, thus the investigation is finalized. During the investigation sEMG signals will be recorded through the EDDI, the seizure detections by the algorithm will be electronically annotated to compare against the times annotated by the staff based alone on the gold standard. The detections of the EDDI will be hidden for the clinical personnel until the end of the admission of the patient. When the admission of the patient has ended, the clinical personnel will remove an SD-card from the A-Unit, and ship it off to the device manufacturer, who will extract the seizure times, and sent them to the principal investigator.

The investigation will be conducted in accordance with the ethical principles that have their origin in the Declaration of Helsinki, ISO 14155 (2011) and the requirements of the local competent authorities.

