#### **3.5.3.2 Exclusion criteria:**

- 1) Suspicion that a patient does not have convulsive epileptic or non-epileptic (PNES) events
- 2) Pregnancy
- 3) Patients known or suspected of not being able to comply with a study protocol (e.g. due to alcoholism, drug dependency or psychological disorder)
- 4) Patients with allergy to the adhesive plaster used to fix the device to the body
- 5) Patients that are involved in other studies.

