## 9. Statistical considerations

#### 9.1 General considerations

A one group design is chosen due to the objective of estimation of sensitivity. No hypotheses are tested, but 95% two sided confidence intervals are constructed for the measure of sensitivity and specificity.

All patients enrolled who has been wearing the device, will be included in the Full Analysis Set (FAS) which forms the basis dataset for all analyses. No subgroup analyses are planned in advance. However if the final data end up showing equally distributed amounts of seizures from both kids and adults, we may study the result in the two subgroups.

The primary endpoint, the sensitivity, will be calculated as described in section 3.5.1 along with a 95% confidence interval (CI). The expectations for sensitivity (true positive assessments) are a lower limit of the two-sided 95% CI of more than  $95\% \pm 5\%$ .

The specificity is calculated and evaluate indirectly as the false detection rate (the number of false detections per hour). This parameter will be estimated along with 95% CI.

The effect of the GTC seizure alarm in a nocturnal situation (23:00 - 07:00) is found. Both the sensitivity and specificity will be calculated based on the data within this period of time (23:00 - 07:00) for each day and analyzed similarly to the analysis of the 24h periods.

Each false alarm is evaluated based on the video data to figure out, what may have caused it.

Adverse events (AEs) are summarized descriptively by type. Please refer to section 16 for details on AE collection types.

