#### 9.2 Sample size consideration for alarm correctness

With an expected sensitivity of 95%, a sample size of at least 19 patients with epileptic GTC seizures is needed. Based on this it has been chosen to include 20 patients with epileptic GTC seizures and furthermore 10 patients with PNES. To succeed in this inclusion, it is expected that about 80 patients will be included in total.

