## 18. Suspension or premature termination of the clinical investigation

Participation in the investigation is strictly voluntary. Subjects are free to discontinue in the investigation at any time with or without giving any reason(s).

A subject is withdrawn from the Investigation in the event of any of the following:

- Withdrawal of consent
- Discontinuation of the monitoring/hospitalization
- Occurrence of a serious or non-serious Adverse Event, Adverse Device Effect or Device Deficiency that in the investigators opinion deems the subjects participation not safe
- No longer in compliance with in- and exclusion criteria
- Subject not in compliance (not able or willing to wear/use the device)

In case of premature withdrawal of a subject, this will be documented in the CRF.

Subject follow-up is performed according to normal clinical procedures after a monitoring/hospitalization period.

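### Sections 8.3 and 9.1 name different populations for the evaluation, and the overall and nocturnal false detection rates depend on which one is used

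*Protocol*

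**What the plan says.** Protocol section 9.1 defines the analysis set: "All patients enrolled who has been wearing the device" are the members, and they "will be included in the Full Analysis Set (FAS) which forms the basis dataset for all analyses". No seizure is required for membership.

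Protocol section 8.3 gives the expected enrolment, "Total number of subjects to be included is expected to be approximately 80", and then says that of these patients "only those with either epileptic GTC seizures or non-epileptic convulsive seizures (PNES) are included in the final evaluation of the EDDI".

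Neither section refers to the other, and neither makes an exception for any endpoint.

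Section 3.5.2 makes the false detection rate a secondary endpoint. It is a count per hour, and an alarm counts as false when it lies outside a seizure period set by the gold standard. A nocturnal version covers 23:00 to 07:00. Section 2.1 names sensitivity and the false detection rate as the two measures of the product's reliability.

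On numbers, section 9.2 says "it has been chosen to include 20 patients with epileptic GTC seizures and furthermore 10 patients with PNES". Section 3.3 expects that "probably 70-80 patients in total will be included and equipped with an EDDI".

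**The concern.** Sensitivity needs only patients who have a GTC seizure. A false alarm rate needs all the time the device was worn, and a patient who has no event contributes nothing but such time. If section 8.3 is followed as written, more than half of the enrolled patients leave the false detection rate, numerator and denominator alike.

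Two things are at stake. The first is precision: the interval is built on a fraction of the hours recorded. The second is how the set is formed. All enrolled patients already need a history suggestive of convulsive events (section 3.5.3.1, criterion 2), so the natural reading of 8.3 is an event observed during monitoring. Membership then depends on an outcome seen after enrolment. Section 3.3 sends the alarm times to the principal investigator, who performs the analysis under section 10.1. With two rules in the protocol, the set could be settled once the alarms are known, and either choice could cite the document.

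**Working it through.** **Inputs**

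- Enrolled: about 80 (sections 8.3, 9.2) or 70-80 (section 3.3).
- Patients with a qualifying event: 20 GTC + 10 PNES = 30 (section 9.2), slightly fewer if some patients have both.
- Observation: 1-4 days per patient (sections 8.4.1, 8.4.2). No mean is given, so the range is used, with equal mean stay in patients with and without events. Equal stay is an assumption.
- Interval: two-sided 95% (section 9.1).

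**The plan's own figure.** The minimum of 19 GTC patients is reproduced by n = 1.96² × 0.95 × 0.05 / 0.10² = 18.25, rounded up to 19. The 10-point half-width is an assumption. This shows where the 20 comes from and does not bear on the conflict.

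**Patients dropped under 8.3**

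- 80 − 30 = 50, or 50/80 = 62.5%.
- 70 − 30 = 40, or 40/70 = 57%.

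**Which endpoints change.** Sensitivity and latency use GTC seizures only, and the PNES measure uses PNES only. Patients with neither add nothing to those counts, so both rules give the same result. The overall and nocturnal false detection rates are the endpoints whose denominators differ.

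**Precision with zero false alarms.** Section 2.1 reports 0/h for the predecessor device and section 7.1.3 expects comparable results, so zero alarms is a relevant case. The exact Poisson upper limit is −ln(0.025)/T = 3.689/T, with T = patients × days × 24 h.

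| | FAS, 80 enrolled | FAS, 70 enrolled | 8.3 set, 30 patients |
|---|---|---|---|
| Hours at 1 day each | 1,920 | 1,680 | 720 |
| Upper limit per hour | 0.00192 | 0.00220 | 0.00512 |
| Hours at 4 days each | 7,680 | 6,720 | 2,880 |
| Upper limit per hour | 0.00048 | 0.00055 | 0.00128 |

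The ratio is 80/30 = 2.67 or 70/30 = 2.33 whatever the length of stay. If each monitored day includes a full 8-hour night, nocturnal hours are one third of these, the limits are three times as high, and the ratios are the same.

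**Precision with some false alarms.** At equal alarm rates the relative standard error is larger under 8.3 by √(80/30) = 1.63, or √(70/30) = 1.53.

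**Bias.** Let k be the alarm rate in patients without events divided by the rate in patients with events. With 80 enrolled, the all-patient rate is (30 + 50k)/80 times the restricted rate.

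- k = 1: 1.00, no change in the estimate.
- k = 2: 1.63.
- k = 0.5: 0.69.

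The documents give no value for k, so the last two lines are illustrations only.

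**The case against.** The best defence is that section 9.1 is the statistical section, names the only defined analysis set and applies it to all analyses. The sentence in 8.3 follows the enrolment total, does not mention the false detection rate, and may only explain why about 80 patients are needed to obtain 20 and 10. That may be what was meant. But the sentence speaks of the final evaluation of the device without exception, and the false detection rate is part of that evaluation. A separate analysis plan might settle the matter, yet the protocol would still contain both rules.

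It is also fair to say that little turns on it formally. The rate is a secondary endpoint, no hypothesis is tested, and no limit is set for it. Even the highest 24-hour limit above, 0.0051/h, is below the 0.04/h that section 2.1 reports for the earlier algorithm. This stands: no stated decision changes.

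A reader might infer three stronger points, which the documents do not support.

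- *That most false alarms would go unreported.* If alarms were spread evenly over 80 patients, 5 in 8 would fall outside the 8.3 set, but that is the case in which the rate itself does not change. Sections 3.5.2, 9.1 and 10.1 also call for each false alarm to be examined.
- *That the narrower set gives a biased rate.* This requires a different alarm rate in patients without events, and neither its size nor its direction is known.
- *That section 18 cuts exposure further.* It lists "No longer in compliance with in- and exclusion criteria" as a ground for withdrawal, and the first exclusion criterion is "Suspicion that a patient does not have convulsive epileptic or non-epileptic (PNES) events". But the flow chart in section 3.5.6 marks eligibility at inclusion only, nothing says it is re-assessed from monitoring results, and section 18 concerns participation. Under section 9.1 a withdrawn patient who wore the device stays in the FAS.

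**Conclusion.** The point holds for the overall and nocturnal false detection rates and for nothing else. Sections 8.3 and 9.1 contradict each other in current text. Following 8.3 would remove 40-50 of 70-80 patients and, with equal mean stay, 57-62.5% of the hours. The upper limit at zero alarms would be about 2.3-2.7 times higher. That loss is certain under 8.3, although its exact size rests on the planned 20 + 10 and on equal stay. Bias remains a possibility that cannot be sized from the documents. Selection on an outcome seen after enrolment, with the choice open until alarms are known, is reason enough to settle the population in advance.

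**What to change.** Replace the restricting sentence in section 8.3 with:

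> *Sensitivity and latency are evaluated in FAS patients with at least one GTC seizure, the PNES measure in FAS patients with PNES, and the false detection rate (24-hour and nocturnal) in all FAS patients over all their monitored hours with the EDDI worn.*

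Take the hours from the monitoring start and stop times in the CRF (section 8.6.1), less any recorded periods with the device off. Section 8.6.1 does not list device on and off times. Where such periods are not recorded, the report should say so, because counting them as exposure lowers the rate. Section 18 needs no change for this point.

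The cost is one sentence, submitted as an amendment under section 11, and video review of false alarms in the additional patients, which section 9.1 already requires. Video, EEG and device recordings are planned for every participant.

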## 3.5.2 Secondary endpoints

- The specificity is calculated and evaluated indirectly as the false detection rate (the number of false detections per hour). A detection is categorized as a false detection, if it falls outside a seizure period (between start and end of a seizure, defined by the gold standard). Possible alarms during placement or removal of the device are discarded (this will only happen if the device is used wrong). All data (incl. video and EEG) are saved for each patient, which makes it possible to find the reasons for possible false alarms.
- Effect of the GTC seizure alarm in a nocturnal situation (23:00 07:00). The sensitivity will be calculated based on the data within this period of time (23:000 07:00) for each day.
- The nocturnal specificity will be calculated as the amount of false positives within the nocturnal period (23:00 07:00) for all days, with respect to the amount of hours.
- For each possible false alarm, the reason for it is checked to see if there is a reasonable explanation.
- The measure for whether the EDDI captures the PNES is calculated as the total number of PNES minus the number of captured PNES and divided by the total number of PNES. This means that a measure close to 100% ensures that the device will not alarm on PNES, and the closer the measure is to 0%, the more false alarms may come from PNES.

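### Sections 8.3 and 9.1 set different populations for the false detection rate; following 8.3 would drop about 40 to 50 of 70 to 80 patients according to their video-EEG result

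*Protocol*

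**What the plan says.** Section 8.3 (Subjects) gives the expected enrolment, "Total number of subjects to be included is expected to be approximately 80", and then states that "only those with either epileptic GTC seizures or non-epileptic convulsive seizures (PNES) are included in the final evaluation of the EDDI".

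Section 9.1 (General considerations) takes every enrolled patient "who has been wearing the device, will be included in the Full Analysis Set (FAS) which forms the basis dataset for all analyses". It goes on to list sensitivity, the false detection rate, the nocturnal versions of both, the review of each false alarm and the adverse event summary.

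Section 3.5.2 measures specificity through the number of false detections per hour: "A detection is categorized as a false detection, if it falls outside a seizure period". It discards alarms raised while the device is being placed or removed.

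On numbers, section 3.3 says "probably 70-80 patients in total will be included and equipped with an EDDI", and section 9.2 says "it has been chosen to include 20 patients with epileptic GTC seizures and furthermore 10 patients with PNES".

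**The concern.** The two sections define two analysis sets, and nothing in the protocol ranks one above the other. This is a contradiction within the protocol, not a detail left for a later analysis plan.

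Section 8.3 cannot be confined to sensitivity by reading it narrowly. Section 2.1 describes the purpose as proving reliability in terms of both sensitivity and false detection rate, and section 8.1 names sensitivity and specificity together as what the investigation assesses. An evaluation of the device therefore includes its false alarms.

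Nor can section 8.3 mean patients merely suspected of convulsive events. Section 3.5.3.1 already requires a suggestive history from everyone. The 30 expected patients among about 80 must be those in whom the event was seen during admission, as judged from EEG and video (section 8.2.2). The restriction thus selects on the reference result after monitoring.

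The excluded patients' hours are ones in which no alarm can be a correct GTC detection, so they matter to a false detection rate. Two analysts who each follow the protocol could report different rates with different precision. Section 3.3 sends the alarm times to the principal investigator, who performs the analysis (section 10.1). If the set is not fixed beforehand, it could be settled with the alarms already known.

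**Working it through.** **Inputs.** Enrolment is about 80 (sections 8.3 and 9.2) or 70 to 80 (section 3.3). The targets are 20 patients with GTC seizures and 10 with PNES (section 9.2). Observation lasts 1 to 4 days, that is 24 to 96 h (section 8.4.1). Intervals are two-sided 95% (section 9.1). Equal stay across patients is an assumption.

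**The plan's own figure.** Section 9.2 asks for at least 19 patients with GTC seizures at an expected sensitivity of 95%. The precision formula n = 1.96² × 0.95 × 0.05 / d² gives 18.25, hence 19, at d = 0.10. That half-width is assumed, because section 9.2 does not state it. The figure concerns sensitivity only; section 9 states no planned precision for the false detection rate.

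**Which results depend on the choice of set.**

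| Result | Patients without GTC seizures or PNES | Differs between 8.3 and 9.1? |
|---|---|---|
| Sensitivity, latency | contribute no GTC seizures | no |
| PNES measure | contribute no PNES | no |
| False detection rate, 24 h and nocturnal | contribute hours and any alarms | yes |
| Review of false alarms | contribute any alarms | yes |

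**Patients removed under section 8.3.**
- 80 − (20 + 10) = 50; 50/80 = 62.5%.
- 70 − (20 + 10) = 40; 40/70 = 57%.
- If all 10 patients with PNES also had GTC seizures, 80 − 20 = 60 would be removed.

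At equal stay, the share of monitored hours lost is the same as the share of patients lost.

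**Precision with zero false alarms.** The exact Poisson upper 95% limit is −ln(0.025)/T = 3.689/T, where T is total hours.

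| Hours per patient | T, 30 patients | Limit per hour | T, 80 patients | Limit per hour |
|---|---|---|---|---|
| 24 | 720 | 0.0051 | 1,920 | 0.0019 |
| 48 | 1,440 | 0.0026 | 3,840 | 0.0010 |
| 96 | 2,880 | 0.0013 | 7,680 | 0.0005 |

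The ratio is 80/30 = 2.67 in every row (70/30 = 2.33 with 70 enrolled). It is the same for the nocturnal rate if night hours are shared in proportion.

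**Precision at equal non-zero rates.** The interval width scales with 1/√T, so it is about √(80/30) = 1.63 times wider under section 8.3 (√(70/30) = 1.53 with 70 enrolled).

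**Point estimate if the groups differ.** The rates here are assumed for illustration and come from no section.
- 0.005/h in the 30 patients with events and 0.02/h in the other 50: section 8.3 gives 0.005/h; section 9.1 gives (30 × 0.005 + 50 × 0.02)/80 = 0.0144/h.
- Reversed: section 8.3 gives 0.02/h; section 9.1 gives (30 × 0.02 + 50 × 0.005)/80 = 0.0106/h.

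**The case against.** The best defence is that section 9.1 is the statistical section and already contains the right rule, while section 8.3 is about recruitment. Its sentence follows directly on the enrolment number and may only explain why about 80 patients are needed to find 30 with events. Data handling fits section 9.1 too: section 3.5.2 keeps data for each patient, and section 10 has the SD-card read for each finished patient, with no filter on seizure status. This stands to the extent that the protocol does not clearly plan to discard these hours. It does not remove the conflict, because section 8.3 speaks of the final evaluation of the device without limiting it to sensitivity.

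A reader might infer that about 50 patients also drop out of the safety summary. The text does not support this. Section 9.1 places the adverse event summary under the full analysis set, and section 16.8 requires every event during the trial to appear in the final report.

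A reader might also infer that section 8.3 flatters the device. That cannot be shown. The direction depends on how false alarm rates compare between patients with and without events, and the protocol gives no such figures.

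Finally, the excluded patients are not necessarily free of seizures. Section 8.6.1 lists tonic, clonic, myoclonic and hypermotor types, and section 3.5.2 refers to a seizure period without saying that it must be a GTC seizure. Whether an alarm during such a seizure counts as false is therefore unsettled, so not every alarm in these patients is plainly a false one.

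**Conclusion.** The contradiction is real and affects the 24 h and nocturnal false detection rates and the review of false alarms. Following section 8.3 removes about 40 to 50 of 70 to 80 patients (57% to 63%) according to the video-EEG result and, at equal stay, a similar share of hours. With zero false alarms, the upper limit is 2.67 times higher on 30 patients than on 80; at equal non-zero rates the interval is about 1.6 times wider. These figures assume that the targets of 20 and 10 are met without overlap, that stay is equal, and that false alarms follow a Poisson process. Any shift in the point estimate has no determinable direction.

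This should be fixed, but it is not critical. The primary endpoint, latency and the PNES measure do not change, safety reporting is intact, no hypothesis is tested, and the false detection rate is a secondary endpoint.

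**What to change.** Replace the restricting sentence in section 8.3 with:

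*Patients with at least one GTC seizure contribute to sensitivity and latency; patients with at least one PNES contribute to the PNES measure; all patients who wore the device (FAS) contribute all monitored hours and alarms, except alarms during placement or removal as in section 3.5.2, to the 24 h and nocturnal false detection rate and the false-alarm review.*

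This brings section 8.3 into line with section 9.1 and keeps the existing rule on discarded alarms. The cost is one sentence in an amendment and a review of false alarms in all wearers. No new data are needed, since EEG and video are recorded on every patient (sections 8.4.1 and 8.4.2). Compared with a rate computed on the section 8.3 patients alone, the reported rate may move in either direction.
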